Criteria	Suitability of the SCRI (Postvaccination Control Window)	Suitability of the CCO	Suitability of the Vaccinated Case- Coverage Design
Outcome is recurrent, and recurrent events are not independent (e.g., stroke)	✓ ^e	✓	✓
Temporal trends in vaccination			
Temporal trends in vaccination are not present during the study period	✓	✓	✓
Temporal trends in vaccination are present during the study period	✓	X	✓

CCO = case-crossover; SCRI = self-controlled risk interval.

Key: Checkmark (✓) indicates design is suitable; X indicates not suitable; O indicates that the study design is possible under certain circumstances.

^a Adapted from Baker et al. [4], Petersen et al. [5], and Madigan et al. [6].

^b Suitable if prodromal symptoms before diagnosis of the outcome do not cause or prevent vaccination, either temporarily or permanently. To address this potential source of bias, every effort should be made to identify the onset of symptoms from the available data such as medical records, rather than relying on the date of diagnosis.

^c The impact of bias due to the potential interference of the outcome on subsequent vaccination could be explored using Farrington’s pseudolikelihood method for censored, perturbed, or curtailed postevent exposures [7].

^d Farrington’s pseudolikelihood method for censored, perturbed, or curtailed postevent exposures should be used to address bias due to censoring of exposures by events [7].

^e If the event can be recurrent, and recurrent events are not independent, only the first event during follow-up should be studied.

8 Research Question and Objectives

Primary objective: To assess the risk of prespecified adverse events << (list the AEs) >> following vaccination with <<specific COVID-19 vaccine product>>

Secondary objectives:

- To assess the risk of prespecified adverse events << (list the AEs) >> in specific vaccine groups defined by platform and/or components (e.g., adjuvant)
- To assess the risk of <<adverse events>> after COVID-19 vaccination by age at vaccination, race, sex, pregnancy status, <<comorbidities>>, <<infections>>, <<concomitant vaccinations>>, <<concomitant medications>>, and <<dose number>>

[Note: If a specific outcome is only relevant to specific subgroups (e.g., multiple inflammatory syndrome would only occur in children), the specific subgroups would be studied in the primary analysis].

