9.2.5.1 Outcome Assessment

In this section, the operational definitions for identifying <<adverse event>> in electronic data should be described, with reference to code lists included in a separate protocol appendix.

[Outcome definitions for the proposed adverse events, including code lists, are currently being developed by another workgroup in this project and will be incorporated in this protocol when they become available.]

<<Adverse event>> will be identified in each participating hospital's discharge database or other electronic data bases using diagnosis codes, or a combination of diagnosis with

procedure or treatment codes in the inpatient, emergency department, or ambulatory speciality care settings. Additionally, electronic laboratory data could be used to identify events, if applicable to the outcome.

For recurrent events in the SCRI design, “washout periods” anchored on the outcome date will be used to identify incident events when multiple visits or codes for the same event occur during follow-up; any events with another event (in any care setting, including inpatient, emergency room, hospital outpatient, or primary care) within the washout period will be excluded. For recurrent events in the case-cross over and vaccinated case-coverage designs, only the first event observed during the study period will be included.

Case validation will be undertaken by clinical reviewers blinded to vaccination status and timing of the event relative to vaccination. Case status and date of outcome onset will be confirmed using medical records, physician questionnaire, or other official documentation (e.g., clinical case notes), depending on the data source. Case status will be determined based on Brighton Collaboration definitions where available [2]. SPEAC is developing a toolbox for case definitions that can be obtained on the Brighton Collaboration website or through the following e-mail address: [contact]. The comparative analysis will only include confirmed cases and the dates of onset assigned by the clinical reviewers.

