 - For persons who receive only one dose, define the risk and control intervals as 1 to 42 and 43 to 127 days after vaccination, respectively.
 - In the above scenarios, the control window could be placed even further in time from vaccination to incorporate a washout period between the risk and control intervals, as needed.
- If there is a short interval between doses of the vaccine but the risk interval is short, a dose-level analysis (treating each dose as a separate observation) could be conducted, but care must also be taken to ensure that the control interval does not overlap with the next dose. For example, suppose the vaccine is administered in two doses approximately 28 days apart, and the outcome of interest has a risk interval of 0 to 7 days. The control interval would need to end before 27 days after vaccination (e.g., 8-15 days) to ensure that there is no overlap of the control interval of the first dose with the risk interval of the second dose.

If the outcome affects the likelihood of a subsequent vaccination after the first dose, the impact of this potential bias could be explored in a sensitivity analysis using Farrington’s pseudolikelihood method for perturbed, censored, or curtailed observation periods for postevent exposures [7].

CCO Design

If the CCO design is used, an exposure window preceding the event will be selected to reflect the period during which exposure to COVID-19 vaccination is hypothesised to trigger the adverse event of interest. A single comparison window preceding the risk window will be selected to reflect the baseline prevalence of exposure; the comparison window should be selected independently of exposure status. Multiple comparison windows per case may also be considered but are not recommended because they may increase the potential for bias due to time-varying confounding and temporal trends in

exposure. By convention, the exposure window will index on the date of the adverse event, which will be time = 0. A washout period between the exposure and comparison windows can be implemented to avoid any carryover effects of the vaccine between the two windows.

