If multiple doses are given during the study, the comparison window should be selected such that the underlying propensity to be vaccinated is not correlated between the exposure and comparison window. This guidance is given because individuals who are vaccinated in both windows do not contribute to the analysis and excluding a large number of individuals due to this reason reduces statistical power and precision of risk estimates. As an example, suppose the vaccine dosing schedule calls for two doses approximately 28 days apart, and the risk window is 1 to 21 days prior to the event. If one were to select a control window of 22 to 42 days, we anticipate that many persons would be vaccinated in both windows and become uninformative to the study. To avoid this, the comparison window could be defined as 50 to 70 days before the event; the comparison window could be placed even further before the event to incorporate a washout period between the exposure and comparison window, as needed.

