Similar to the SCRI, the CCO is a case-based study in which each person serves as his or her own control. However, the primary distinguishing feature of the two designs is that the CCO follows the conceptual framework of the case-control study, with events fixed and exposure random [4,22]. The design compares the odds of exposure in a window, during which it is hypothesised to trigger the adverse event to that in a control period, which represents the baseline odds of exposure. The study design is traditionally unidirectional, with the comparison window preceding the risk window in time, so as to avoid bias due to reverse causation (Figure 3-2). Only cases vaccinated in either the exposure or comparison window (not both windows) are informative for the analysis. Therefore, follow-up after events (i.e., hospital discharge) is not needed. The design is well suited to study single or multiple exposures as well as rare events.

Like the SCRI, the CCO can adjust for time-varying confounders if the appropriate data are available. However, unlike the SCRI, the CCO is biased if there are temporal trends in exposure. It is highly plausible that a person's likelihood of COVID-19 vaccination will change over time, as the vaccine will be new and likely highly desirable, and availability and vaccine recommendations may change over time. Additionally, the CCO may be subject to within-person protopathic bias and confounding by indication (or contraindication) if prodromal signs of the outcome prior to diagnosis of the event cause (or prevent) vaccination.

Figure 3-2. Case-Crossover Study Design

T = time in days.

Note: In this example, the risk window is 1 to 42 days before the adverse event.

Vaccinated Case-Coverage Design

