Annex 5. Feasibility Questionnaire

General Questions

1. Name of data source: _____
2. Contact person: _____
Institution: _____
E-mail address: _____
Phone number: _____

Outcomes

3. Does your site have a hospital discharge database that captures diagnoses and procedures?
___ Yes
___ No → Stop, thank you for your time
4. Does your site distinguish primary diagnoses from the other diagnoses?
___ Yes
___ No
5. Number of patients treated by your hospital annually:

6. Number of patients treated by your hospital annually for the following outcomes:
 - a. [Outcome A]: _____
 - b. [Outcome B]: _____
 - c. etc
7. What is the geographic area covered in the catchment area for your hospital?

8. What is the population coverage of your hospital?

9. How often are your hospitalisation data refreshed and made available for research?

10. How long is the data lag of the hospitalisation records, that is, how much time passes after hospitalisation before the data are available for research purposes?

11. What is the earliest date of data captured by your hospitalisation data?

12. Are the calendar dates of the hospitalisation available?

Yes, the admission and discharge date are available

Yes, the diagnosis date is available

Yes, other. Please specify: _____

13. Can your site identify diagnoses made in the hospital setting of the following outcomes?

a. [Outcome A]? Yes No

b. [Outcome B]? Yes No Etc.

14. What coding system does your site use for diagnosis in the hospital setting?

15. Does your site have the ability to validate outcomes and dates of outcome onset through the use of medical record review, physician questionnaires, case notes, or other methods?

Yes

No

16. What method can you use to validate outcomes and date of onset?

Medical record review

Physician questionnaire

Case notes

Other, please specify: _____

Exposure

17. Can your site identify receipt of COVID-19 vaccines through linkage with other data?

Yes

No → Stop, thank you for your time.

Note that for this study, primary data collection or other self-report information on vaccinations is not acceptable.

18. To what type of exposure data does your site have access (check all that apply)?

Vaccine registry

Primary care records

Pharmacy dispensing data

Patient vaccination cards

Hospital-based medical records

Other, please specify: _____

19. What is the population coverage of the vaccination data source?

20. What is the geographic area covered by the vaccination data source?

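### For outcomes that can begin during an unrelated hospital stay, no rule covers the inpatient days before onset, which can pull estimates towards or below the null

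*Protocol*

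**What the plan says.** Section 9.2.5.1 identifies cases in hospital electronic data by diagnosis codes, alone or together with "procedure or treatment codes in the inpatient, emergency department, or ambulatory speciality care settings". Blinded adjudicators then settle case status and timing: "The comparative analysis will only include confirmed cases and the dates of onset assigned by the clinical reviewers".

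For the CCO, section 9.2.5.3 states: "By convention, the exposure window will index on the date of the adverse event, which will be time = 0". Its worked example supposes that "the risk window is 1 to 21 days prior to the event" and suggests that "the comparison window could be defined as 50 to 70 days before the event". The note to Figure 3-2 in Annex 3 uses a longer window: "In this example, the risk window is 1 to 42 days before the adverse event". Section 9.2.5.4 applies the same window guidance to the vaccinated case-coverage design.

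The inclusion criteria in 9.2.3.1 and 9.2.3.2 do not limit cases to community onset, presence at admission or a primary diagnosis. Annex 4 rates ARDS, acute kidney injury, thrombocytopenia and the groups containing arrhythmia, pulmonary embolus and deep vein thrombosis as suitable for all three designs, without comment. The nearest safeguard is Table 1, footnote b: "Suitable if prodromal symptoms before diagnosis of the outcome do not cause or prevent vaccination, either temporarily or permanently". Annex 5 asks sites which dates they hold, and one answer is "Yes, the admission and discharge date are available". No case rule uses that answer.

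**The concern.** A patient admitted for one reason may develop one of these outcomes some days later. The days just before onset were then spent in hospital. If few people are vaccinated there, those days add length to the exposure window but hardly any chance of a dose. The comparison window, several weeks earlier, is not affected. Doses are therefore depleted on one side only.

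The safeguards in the protocol do not reach this:

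- Footnote b concerns symptoms of the outcome itself, not an admission for something else.
- Section 9.2.5.5 names age, calendar time, infections and other vaccines as time-varying confounders. It does not name a current hospital stay.
- The case-coverage reference strata are matched on factors such as age, sex and risk conditions. They are not matched on being in hospital, so the offset does not correct the loss.
- Sections 9.6.5 and 9.8 do not mention the issue.

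What is at stake is a safety signal that looks weaker than it is or, with no true effect, an apparent protection. Collecting more cases does not remove the bias. In one scenario Table 2 offers the SCRI as a check on bias in the CCO. Because the SCRI leans the same way here, agreement between the two would not be reassuring on this point.

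**Working it through.** The protocol gives no figure for this bias. Its only related figures are the case numbers in Table 3 (section 9.4), so these are reproduced first and then used to show the cost in power.

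**1. Table 3.** For r, the proportion of time in the risk interval, and relative incidence ρ:

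- p = ρr/(ρr + 1 − r)
- A = 2[p ln ρ − ln(ρr + 1 − r)]
- B = (ln ρ)²/A × ρr(1 − r)/(ρr + 1 − r)²
- n = (z₁ + z₂√B)²/A

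Power is 80% as stated. The significance level is not stated; two-sided 5% is assumed. With r = 0.5 and ρ = 2: p = 0.667, A = 0.1133, B = 0.943, and n = (1.960 + 0.842 × 0.971)²/0.1133 = 68.1, rounded up to 69 as printed. All 15 cells match (33% entered as 0.33), so the table is not at fault. A CCO with one comparison window as long as the exposure window corresponds to r = 0.5.

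**2. Inputs for the bias.**

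- W = 21 and W = 42 days are the protocol's CCO examples. W = 7 comes from the short risk interval in 9.2.5.3, which is given there for the SCRI and is used here as a short CCO window.
- s (share of hospital-onset cases, 10–50%) and L (inpatient days before onset, 3–10) are assumptions. The documents give neither.
- Also assumed: no vaccination on inpatient days, a constant vaccination rate outside hospital, equal windows, and a comparison window untouched by the stay.

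**3. Formula.** A community-onset case has W days of opportunity in each window. A hospital-onset case has W − min(L,W) days in the exposure window and W in the comparison window. Hence

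expected OR = RR × [(1 − s)W + s(W − min(L,W))]/W = RR × [1 − s·min(L,W)/W].

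**4. Results.** Columns 3 to 6 use s = 30% and L = 5; columns 4 to 6 also use a true ratio of 2.

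| W (days) | Factor, s = 10–50%, L = 3–10 | Factor | Expected OR | Power with 69 cases | Cases for 80% power |
|---|---|---|---|---|---|
| 42 | 0.88–0.99 | 1 − 0.3×5/42 = 0.964 | 1.93 | 76% | 76 |
| 21 | 0.76–0.99 | 1 − 0.3×5/21 = 0.929 | 1.86 | 71% | 85 |
| 7 | 0.50–0.96 | 1 − 0.3×5/7 = 0.786 | 1.57 | 46% | 157 |

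Over the full ranges, a true ratio of 2 appears as 1.76–1.99 (W = 42), 1.52–1.97 (W = 21) and 1.00–1.91 (W = 7). The value 1.00 needs s = 50% and L of at least 7. Simulation of the three tabulated scenarios and of W = 7, s = 50%, L = 7 gave 1.93, 1.86, 1.57 and 1.00. With no true effect the factor is itself the expected odds ratio.

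**5. Dependence on the assumptions.** If inpatients are vaccinated at a fraction v of the community rate, the loss is multiplied by 1 − v. At v = 0.5, W = 21, s = 30%, L = 5 the factor is 1 − 0.3×0.5×5/21 = 0.964 instead of 0.929. If L varies between cases, short windows lose less. With L exponential with mean 10 and W = 7, the mean of min(L,W) is 10(1 − e^−0.7) = 5.03, so at s = 30% the factor is 1 − 0.3×5.03/7 = 0.78 rather than 0.70.

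**6. SCRI.** An event with onset after L inpatient days cannot fall within the first L days after a community dose. Those days lie in the risk window, so its event count is depleted while a later control window is not. The direction is the same; no size was calculated.

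**The case against.** This is a template. Outcome definitions and code lists are still to come, the confounder list is left to the investigator, and a present-at-admission rule could be added there. Indexing on the event is also normal CCO practice. Both points are fair: the quoted sentence is not an error, and the gap is the missing case rule beside it. But case identification and indexing are written as settled text, and section 8 lets investigators keep some wording unchanged. A study that does so inherits the gap without a prompt.

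The protocol also handles part of the problem. Adjudicated onset moves the index date back where the admission was for early signs of the same illness, infections are adjusted for, and 9.8 concedes time-varying confounding. None of this removes inpatient days due to an unrelated admission.

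A reader might infer that real risks are hidden in general, or that every design at every site is affected. The documents do not support either. They do not say whether inpatients are vaccinated, and they give no s or L. With the protocol's own 21- and 42-day CCO windows the loss is about 1–24% over the ranges tried, which is attenuation. For outcomes that seldom begin in hospital it is negligible.

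A reader might also infer that every event with onset after admission should be excluded. That would go too far. It would drop cases in which a possibly vaccine-triggered illness led to the admission and the outcome followed in hospital.

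**Conclusion.** The point holds for outcomes that can begin during a stay for another reason. As written, the plan includes these cases, runs the CCO and case-coverage windows back from onset, and has no rule for the inpatient days in between. The bias is towards or below the null in both designs, and in the SCRI as well. It is modest for long windows (at most about 12% at 42 days and 24% at 21 days over the ranges tried). It becomes serious when the window is short and hospital onset is common (up to half the odds ratio at 7 days). The missing rule can be read from the text. The size rests on assumed values of s and L and on rare vaccination in hospital, and it shrinks in proportion if inpatients are vaccinated. The change is worth making because it alters a result and needs little extra data.

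**What to change.** - **9.2.4 and 9.2.5.1:** add admission date to the outcome eCRF. Have the blinded adjudicators put each event in one of two groups: (a) present at admission, or part of the illness that led to admission; (b) arising during a stay for an unrelated reason. Because they do not know vaccination status or timing, the classification cannot be steered by exposure. Set in advance how unclear cases are assigned.
- **Primary analysis, all three designs, for the outcomes concerned:** use group (a). In the model above this removes the lost opportunity, and the expected odds ratio returns to its true value.
- **9.6.5:** report the all-onset result and, for the CCO and case-coverage designs, a version with windows indexed on admission. The latter keeps the group (b) cases but reaches further back from onset (with W = 7 and L = 10, to days 11–17). It can therefore miss part of the true risk window and suits a sensitivity analysis better than the primary one.

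The cost is one date, which Annex 5 already asks sites about, one extra adjudication item and the added analyses. The downside is that group (b) cases are lost from the primary analysis, with some loss of precision where they are common.

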If the vaccine is administered in multiple doses, then each exposure code will be considered to be a separate instance of vaccination, provided that sufficient time has passed between the dates of the codes, based on the vaccine dosing schedule and taking into account the possibility that some persons may receive subsequent doses slightly earlier than indicated in the vaccine dosing schedule (for example: if the vaccine dosing schedule calls for two doses at least 28 days apart, then any code for vaccination that occurs fewer than 21 days after the first code would be excluded, under the assumption that any additional codes after the first code are duplicates of the same dose). If the vaccine is administered as a single dose, then only the first exposure code during the study period will be considered, which assumes that the remaining codes are errors.

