9.6.4 Subgroup Analysis

If relevant to specific adverse events, the presence of effect modification by relevant variables (dose number, age at vaccination, specific comorbidities, concomitant vaccinations) will be assessed by adding an interaction term between vaccination and the effect modifier of interest to regression models for the CCO and SCRI designs. Effect modification will be assessed in the vaccinated case-coverage design by adding the potential effect modifier as a covariate to the regression model.

Subgroup analysis will be performed by strata of effect modifiers of interest as relevant. For the vaccinated case-coverage design, subgroup analysis will require that the at-risk-stratum for calculating the expected odds of vaccination be redefined based on the different subgroups.

[The study investigator(s) should describe subgroups motivated by the current understanding of the study outcomes in this section.]

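### Excluding cases vaccinated in both case-crossover windows costs only power for the any-dose odds ratio, but biases the planned dose-number analysis

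*Protocol*

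**What the plan says.** The CCO text in Protocol Section 9.2.5.3 advises choosing the comparison window so that vaccination propensity is uncorrelated between the two windows. The reason given is that "individuals who are vaccinated in both windows do not contribute to the analysis and excluding a large number of individuals due to this reason" costs power and precision. Annex 3 (Case-Crossover Design) states the same rule: "Only cases vaccinated in either the exposure or comparison window (not both windows) are informative for the analysis".

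The worked example reads: "suppose the vaccine dosing schedule calls for two doses approximately 28 days apart, and the risk window is 1 to 21 days prior to the" adverse event. It then says "If one were to select a control window of 22 to 42 days, we anticipate that many persons would be vaccinated in both windows", and offers a remedy: "To avoid this, the comparison window could be defined as 50 to 70 days before the event". The window may be moved further back to allow a washout.

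Dose number is among the secondary-objective factors in Section 8. Section 9.2.5.5 says it will be assessed as an effect modifier. Section 9.6.4 does this by "adding an interaction term between vaccination and the effect modifier of interest to regression models for the CCO and SCRI designs". The CCO estimator in Section 9.6.2 is conditional logistic regression with one stratum per case.

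**The concern.** Dose order is fixed. A case vaccinated in both windows therefore always has dose 1 in the earlier (comparison) window and dose 2 in the later (exposure) window. Excluding such cases removes dose-1 exposures only from the comparison side and dose-2 exposures only from the exposure side. The two losses cancel in an any-dose contrast but not in a dose-specific one.

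If the exclusion is carried into the dose-number analysis, a vaccine with no effect can show apparent first-dose harm and second-dose protection, and a real second-dose risk can be understated. The SCRI part of the same section warns that each dose can confound the other. The CCO part has no such warning.

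**Working it through.** **Inputs.** Exposure window of days 1–21, rejected comparison window 22–42, suggested comparison window 50–70, and doses about 28 days apart: all from Section 9.2.5.3. Assumed, because the protocol gives neither: the spread of dose gaps, and that everyone completes dose 2 unless stated. Uptake is constant.

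**The protocol's own example.** For a dose gap of g days, let k be the number of the 21 comparison-window days on which a first dose has its second dose in days 1–21, and let f = k/21.

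- Window 22–42, g = 28: dose 1 must fall on days 29–42, so k = 14 and f = 14/21.
- Window 50–70, g = 28: dose 1 would have to fall on days 29–49, so k = 0.

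The example is reproduced: many overlaps with the first window, none with the second.

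**Effect of exclusion.** Let R1 and R2 be the true relative effects. Counts per uptake day, with both-window cases dropped:

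- Dose 1: 21·R1 in the exposure window and 21 − k in the comparison window, so OR1 = R1/(1−f).
- Dose 2: (21 − k)·R2 and 21, so OR2 = R2·(1−f).
- Any dose, R1 = R2 = R: R·(42 − k)/(42 − k) = R, which is unbiased.

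**Null results, window 50–70.** k = g − 28 for gaps of 29 to 49 days.

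| Gap (days) | k of 21 | Dose-1 OR | Dose-2 OR | Any-dose OR |
|---|---|---|---|---|
| up to 28 | 0 | 1.00 | 1.00 | 1.00 |
| 29 | 1 | 1.05 | 0.95 | 1.00 |
| 30 | 2 | 1.11 | 0.90 | 1.00 |
| 32 | 4 | 1.24 | 0.81 | 1.00 |
| 35 | 7 | 1.50 | 0.67 | 1.00 |

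Beyond a 49-day gap the overlap shrinks, and it ends at 70 days. A simulation of 4 million persons gave 1.50, 0.67 and 1.00 at 35 days. For the rejected 22–42 window at 28 days it gave 3.02, 0.33 and 1.00.

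**Assumed spreads of gaps, evenly distributed.**

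- 25–31 days: mean k = (1 + 2 + 3)/7 = 0.857, f = 0.041, ORs 1.04 and 0.96.
- 28–35 days: mean k = (0 + 1 + … + 7)/8 = 3.5, f = 0.167, ORs 1.20 and 0.83. If only 80% complete dose 2, the dose-1 OR is 1/(1 − 0.8 × 0.167) = 1.15 and the dose-2 OR is unchanged.

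**Keeping the cases.** Enter dose 1 and dose 2 as separate indicators. A both-window case is then discordant by dose and informs the difference between the two log odds ratios. At the null this gives 1.00 and 1.00 at every gap tested.

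Away from the null it is not exact. The reverse pattern (dose 2 first) cannot occur, so the two windows are not exchangeable for these cases. With true ORs 3 and 3 and f = 1/3, the counts are 63 and 14 for dose 1, 42 and 21 for dose 2, and 21 in both windows. Maximum likelihood gives 2.48 and 3.90. Check of the dose-1 score equation: 77 × 2.48/3.48 + 21 × 2.48/6.38 = 54.9 + 8.2 ≈ 63. Dropping the cases gives 3/(2/3) = 4.5 and 3 × 2/3 = 2.0.

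**The case against.** The strongest reply is that the harmful analysis may never be run. An interaction model as in Section 9.6.4, fitted by conditional logistic regression, uses a dose-2-versus-dose-1 case automatically, and nothing says such cases are deleted before that model is fitted. This stands: the bias arises only if the exclusion is applied to the dose-number analysis. But then the statement in Section 9.2.5.3 and Annex 3 that these cases contribute nothing is itself wrong for that model, so the sections need aligning either way.

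Second, for the any-dose OR a loss of power is the right description. This stands fully when the doses have the same effect. When they differ, the pooled value is reweighted towards dose 1: with true ORs 1 and 3 and f = 1/3 it is (1 + 2)/(0.667 + 1) = 1.8, against an equal-weight average of 2.0.

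Third, the 50–70 window is an illustration for doses about 28 days apart. It is worded as a possibility, can be moved back, and sits under a rule about uncorrelated propensity. Section 9.2.5.2 has an example with "if the vaccine dosing schedule calls for two doses at least 28 days apart", but that concerns duplicate vaccination codes. Most of this stands. What remains is that the rule is justified by power and the move by washout. Neither is tied to the spread of dose gaps, and the example has no margin for a gap above 28 days.

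**Conclusion.** Describing the exclusion as only a loss of power is correct for the any-dose contrast with equal dose effects, and incorrect for dose-specific CCO results. There it multiplies the two ORs by 1/(1−f) and (1−f), in opposite directions, even when the vaccine has no effect.

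The size depends on dose gaps that the protocol does not give. It is about 4% for an assumed spread of 25–31 days. For 28–35 days the dose-1 OR is 20% too high and the dose-2 OR 17% too low.

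A reader might infer that the CCO's main estimate is invalid, or that the 50–70 example collapses once a second dose comes after day 28. The protocol supports neither. The any-dose OR stays at its true value when the doses act alike. The example does what it claims at 28 days, and the distortion then grows gradually from 1 day in 21. Large distortions, such as those at 35 days, need gaps well beyond the example's premise.

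Severity is moderate, confined to dose-specific results of a multidose CCO.

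**What to change.** - **Section 9.2.5.3 and Annex 3:** limit the statement that both-window cases do not contribute to the any-dose contrast, and say that excluding them biases dose-specific estimates.
- **Section 9.6.4:** keep both-window cases in the CCO dose-number model, with dose 1 and dose 2 as separate exposure indicators. Report how many there are, and do not report dose-specific ORs with them dropped. State that this model is exact at the null and otherwise only less biased.
- **The 50–70 example:** present it as valid for dose gaps up to 28 days. Prespecify window placement from the expected spread of gaps in programme or schedule data. Do not take it from the cases, because Section 9.2.5.3 requires the comparison window to be chosen independently of exposure status. With exposure window 1–21, the first overlapping gap is the window's start day minus 21: 36 days for 57–77, 43 for 64–84, 50 for 71–91.

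The cost is protocol wording and one coding rule. A more distant window needs a longer exposure look-back and is more open to uptake trends. Section 9.1 favours a control window close in time for that reason, so the two must be weighed. Retention leaves some bias if overlap is common and the effects are not null, which is why window placement matters as well.
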